- 100 2. Patients who are currently on medications that suppress the immune system.

- 109 3. Patients who do not have at least 2 trigger foods identified.
110 4. Patients who have a history of an organic GI disease (e.g., inflammatory bowel disease, celiac
111 disease, biliary disorders, bowel resection), cardiac, pulmonary, neurologic, renal, endocrine, or
112 gynecological pathology
113 5. Lack of parental or guardian informed consent.

114
115 Study Design

- 118 1. Potential participants will be contacted by email and / or telephone after pre-screening of physician-
119 diagnosed FPIES patients who have visited the UM allergy clinics within the past three years, or who
120 are currently in contact with the UM allergy clinic nutritionist. An option for the patients to opt out will
121 be provided. The patient's primary allergist or pediatrician will be informed about study team's
122 contact with the identified patients. Patients may be referred by their primary allergist during a clinic
123 visit.
124 2. If a parent/guardian expresses interest in the study, they will be sent/given a copy of the informed
125 consent to review.
126 3. An appointment will be scheduled with a study team member at the UM allergy clinics.
127 4. The protocol will be discussed face-to-face with parent/guardian with an opportunity to ask questions
128 and review the informed consent document. After written informed consent is signed by one
129 parent/guardian, study procedures can begin. Parent/guardian will be given a copy of the signed
130 informed consent and it will be imaged into the chart.
131 5. Parent/Guardian will be asked to fill out Questionnaire One at the time of entry into the study.
132 6. Parent/Guardian will be instructed regarding scheduling the blood draw for analysis:
133 a. Only known "safe foods" (foods that do not induce repetitive vomiting) are to be consumed
134 for one week before blood draw.
135 b. Blood draw will be performed at the MLabs Blood Draw Stations at Michigan Medicine
136 outpatient clinics.
137 7. Patient will have 6 ml of blood drawn for analysis:
138 a. 5.5 ml of blood for testing of potential food reactions
139 b. 0.5 ml of blood for RNA/DNA analysis, which will be stored.
140 8. After blood draw, diet will be managed per the primary clinician and nutritionist.
141 a. Parents will be given Questionnaire Two to fill out detailed information about all foods
142 introduced until the results of the assay are received.

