143 b. During that time, food introduction will continue as directed by primary allergist and/or
144 nutritionist
145 9. Blood will be analyzed by the PI in a research lab at the University of Michigan to determine
146 differences in the PI's assay between potentially tolerated and not tolerated foods (see description of
147 laboratory test lines 216-232)
148 10. After identification of potentially "safe foods" to be introduced in the future, the information will be
149 given to the clinical study team and child's clinician, who will contact parents by phone or email
150 (parental preference).
151 a. Parents will be asked to detail current nutritional status, including foods tolerated or not
152 tolerated since the initial blood draw. Results will be recorded by the study team and the
153 parents will be asked to return Questionnaire Two.
154 b. After discussion within the clinical team (including clinical research team and child's
155 clinicians), parents will be instructed to introduce new foods identified as potentially safe into
156 the diet, one at a time for seven days.
157 c. Results of these trials will be recorded on Questionnaire Three and returned to the study
158 team 3 month intervals.

159 11. A second blood draw will be performed, at least 2 weeks after the initial blood draw. 6 cc will be
160 drawn:

- 161 a. To explore the consistency of a standard panel of foods vs individually prepared foods
- 162 b. To perform additional analyses including single cell RNASeq (scRNA-seq) on WBCs
- 163 following treatment with foods.

164 12. Subjects will be followed at 3 month intervals with review of tolerated foods, number and types of
165 known triggers assessed. When a subject is tolerating two or more triggers foods for 3 or more
166 months:

- 167 a. Questionnaire Four will be given to fill out and return
- 168 b. Subject will have 6 mL drawn for analysis
 - 169 i. 5.5 mL to rerun the initial assays
 - 170 ii. 0.5 mL for RNASeq on WBCs following treatment with foods.

171 Study Grid

	Baseline visit - Day 0	Lab Day 0- 14	Lab >2 weeks after initial blood draw	At home 1-3 months	3 up to 36 months	At home every 3 months up to 36 months	> 2 trigger foods tolerated
Consent	X						
Questionnaire 1	X						
Blood Draw		X	x				X
Phone/email/in-person to inform of potentially tolerated foods.				X			
Questionnaire 2				X			
Testing Foods Found as tolerable					X		
Questionnaire 3						X	
Questionnaire 4						X	X

172
173 B. Sources of Materials

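### The team that records interval food outcomes already holds the assay's list of potentially safe foods, and Questionnaire Two is requested only after that list is released

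*Combined protocol and SAP*

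**What the plan says.** All references are to section I.1.A of the combined protocol and SAP.

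- **Study Design, step 8a.** After the first draw, "Parents will be given Questionnaire Two to fill out detailed information about all foods" "introduced until the results of the assay are received". Parents hold the form, and its coverage ends when the result arrives.
- **Step 8b.** "During that time, food introduction will continue as directed by primary allergist and/or" the nutritionist. The assay does not choose these foods.
- **Step 10.** Once the PI's laboratory has identified potentially safe foods, the information is "given to the clinical study team and child's clinician, who will contact parents by phone or email".
- **Step 10a.** Parents are asked for current nutritional status, including foods tolerated or not "tolerated since the initial blood draw. Results will be recorded by the study team and the" "parents will be asked to return Questionnaire Two".
- **Steps 10b and 10c.** Parents then introduce foods identified as potentially safe. "Results of these trials will be recorded on Questionnaire Three and returned to the study" team.
- **Study Grid.** The contact row reads "Phone/email/in-person to inform of potentially tolerated foods". It and Questionnaire 2 are both marked in the at-home, 1–3 month column.
- **Statistical Design.** The outcome is binary (safe or trigger food). The assay counts as predictive if the lower 95% limit of the clustered AUC exceeds 0.5. The source of the safe/trigger label is not stated.

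The documents describe no blinded recorder, no return of Questionnaire Two before release, no lock on its entries and no rule for settling unclear trials.

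**The concern.** Aim 1 is to show that the assay separates safe from trigger foods. The fairest test uses foods introduced after the draw, chosen without the result, with the outcome recorded by someone who does not know the result. Questionnaire Two meets the first two conditions. The order in steps 10 and 10a gives up the third for the study team's own record and does not protect it for the parents' form.

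The outcome is a caregiver's account of a young child's symptoms, relayed by phone or email. The only working description of a safe food is one that does not cause repetitive vomiting. A food stopped early, or a reaction described vaguely, leaves room for judgement. A recorder who knows the food is on the safe list may settle such a case as tolerated. That would raise agreement between assay and outcome whether or not the assay works. With a success threshold of 0.5 for the lower limit, even modest drift could matter.

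**Working it through.** **1. Order of events**

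| Event | Step | Who holds the assay result |
|---|---|---|
| Parents receive Questionnaire Two; foods chosen by usual clinicians | 8a, 8b | No one |
| Laboratory analysis | 9 | PI's laboratory |
| List of potentially safe foods released | 10 | Clinical study team and child's clinician |
| Tolerated/not tolerated since draw asked and recorded; Questionnaire Two requested | 10a | Study team: yes. Parents: not stated |
| Assay-selected foods introduced; Questionnaire Three | 10b, 10c | Everyone |

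The team's record therefore follows its receipt of the list. Return of the form also follows release. When parents write their entries is not fixed.

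**2. Are these the only unsteered prospective outcomes?** Questionnaire One is completed at entry, before the draw. Questionnaire Three covers foods the assay called potentially safe. Questionnaire Four is triggered once former trigger foods are tolerated. Only the interval in step 8 yields prospective outcomes for foods chosen without the assay.

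**3. Illustrative size.** The plan has no figure to reproduce: it gives up to 20 children, with no power, target AUC or foods per child. All inputs below are assumptions.

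Take a call unrelated to the truth, half of foods called safe, true reaction rate p, and a share e of trials equivocal and recorded to match the call. AUC is the mean of sensitivity and specificity.

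- Sensitivity = [(1−e)p/2 + e/2] / [(1−e)p + e/2]
- Specificity = [(1−e)(1−p)/2 + e/2] / [(1−e)(1−p) + e/2]

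For p = 0.2, e = 0.10: sensitivity = 0.14/0.23 = 0.609, specificity = 0.41/0.77 = 0.532, AUC = 0.571.

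| | e = 5% | e = 10% | e = 20% |
|---|---|---|---|
| p = 0.2 | 0.537 | 0.571 | 0.630 |
| p = 0.1 | 0.559 | 0.604 | 0.669 |

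**4. Two milder versions**

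*One direction only.* Step 10 releases a safe list. Suppose equivocal foods on it are recorded as tolerated, while equivocal foods off it are recorded as reactions at the ordinary rate p. Then:

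- Sensitivity = (p/2) / [p(1 − e/2)] = 1/(2 − e)
- Specificity = [(1−e)(1−p)/2 + e/2] / [(1−e)(1−p) + e/2 + e(1−p)/2]

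For p = 0.2, e = 0.10: 1/1.9 = 0.526 and 0.41/0.81 = 0.506, AUC = 0.516. For e = 5% and 20% the AUC is 0.508 and 0.534.

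*Dilution.* If interval foods supply a quarter of all labels and 10% of those are relabelled in both directions, then e = 0.25 × 0.10 = 2.5% overall. With p = 0.2: 0.11/0.2075 = 0.530 and 0.4025/0.7925 = 0.508, AUC = 0.519.

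**5. Effect on the success rule.** Simulation with 20 children, a useless continuous score, 30% true triggers, 40% called trigger, foods independent within child, the Obuchowski clustered variance and 3,000 runs per setting. A share d of outcomes that disagree with the call is re-recorded to match it, in both directions. Chance that the lower 95% limit exceeds 0.5:

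| Foods per child | d = 0 | d = 0.1 | d = 0.2 | d = 0.3 |
|---|---|---|---|---|
| 4 | 3.6% | 15% | 39% | 67% |
| 8 | 3.2% | 22% | 63% | 92% |
| 12 | 3.4% | 31% | 78% | 99% |

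Mean AUC is about 0.50, 0.56, 0.61 and 0.66 across the columns. These runs take every label from the drifting source and score the assay directly, not through the planned nine-marker logit model.

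**The case against.** The case against has real force on four points.

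- **Parents may record in time.** A reader might infer that every Questionnaire Two outcome is written down after the result is known. The documents do not support that. Step 8a has parents fill in the form during the interval, and step 10a comes before the instruction in 10b, so parents may answer before hearing the list. A shared grid column shows a common window, not a sequence. What stands is that the form comes back only after release and that nothing rules out late or revised entries.
- **The team may not know a call for each food.** A reader might infer that it does. Step 10 passes on potentially safe foods for future introduction. It does not say that trigger calls are passed on or that foods already tried are included. But the plan does not exclude interval foods from the list, and the team asks which foods were introduced only in step 10a, so overlap is possible.
- **The wording limits ambiguity.** If a reaction means repetitive vomiting, a single vomit does not make a food a trigger. This narrows the room for judgement without removing it, since no rule covers early stopping or unclear histories.
- **The label source is unstated.** Every child enters with at least two trigger foods documented before the assay, and those labels cannot drift in this way. If they dominate the analysis, the effect is diluted, as the quarter-share calculation shows.

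None of these points changes the fact that the study team makes its own interval record while holding the result.

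**Conclusion.** The point holds as an avoidable risk of bias created by the stated order of steps 10 and 10a. It is established for the study team's own record and for the timing of the form's return; for the parents' entries it is only left open. A reader might go further and infer that the trial's AUC will be inflated by a known amount. The documents do not support that, because they give neither the share of equivocal trials, nor the foods per child, nor the source of the safe/trigger label.

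Under the stated assumptions, a useless assay at a 20% reaction rate would show an AUC of 0.54–0.63 with two-way drift in 5–20% of trials, and 0.51–0.53 if only foods on the safe list are affected. The change should be made: the uninformed record costs little to obtain before release and cannot be recovered afterwards.

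**What to change.** Rewrite step 10 in this order:

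1. Before the laboratory releases anything, obtain Questionnaire Two and the step 10a status update from the parents.
2. Have a clinical team member enter each interval food as tolerated or not tolerated, and lock the entry with a date stamp in the REDCap 'Research Data' database. That database is also listed as holding blood test results, so load the child's assay result only after the lock.
3. Then release the result to the clinical study team, the child's clinician and the parents.
4. If the form is not back by a set date, take the status update by phone or email, lock it, and release.
5. Keep interval foods reported after release under Questionnaire Two and flag them as unlocked. Moving them to Questionnaire Three would mix unsteered foods with assay-selected ones.

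In the Statistical Design, state which outcomes supply the safe/trigger label for the AUC and how unlocked entries are handled.

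The cost is a wording change and one database lock. No visit, blood or staff is added, because the existing clinical team does not have the result until release. The downside is that release may be slightly delayed; the set date keeps an unreturned form from holding it up.

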202 distinct time points. Only study team members will have access to this data.

- 203 1. A master list that includes identifiable data will be kept in a REDCap "Study Housekeeping"
204 database that includes subject number, patient name, parent names, MRN, contact information
205 including address, email, phone number, documentation of blood draw, samples saved and filling
206 out of questionnaires.
- 207 2. All data variables will be kept in a separate "Research Data" REDCap database. Subjects will be
208 identified only by subject number in this database. Data will include:
- 209 a. Results of blood tests
210 b. Questionnaire answers
211 c. Age
212 d. Number of food reactions
213 e. Identified trigger foods
214 f. Identified tolerated foods.
- 215 3. Data downloaded for analysis will have only subject number included.
- 216 4. Stored RNA, DNA or cDNA samples will contain only the subject number without personal
217 identifiers.
- 218 5. Parents/guardians may request that stored blood samples be destroyed at the end of the study.

219 **C. Potential Risks**

220 **Describe potential risks**

221 The risk in this study arises due to incorrect predictions by the test. The current test being validated is not
222 an FDA-approved or cleared test. However, current standard of care recommends which foods to trial in a
223 random fashion, and incorrect predictions frequently occur leading to reactions. Hence this study will not
224 pose an added risk to the current standard of care. The indication of what to trial will be communicated to
225 the patients by the allergist and nutritionist as currently occurs in the standard of care. However, the only
226 difference is that the allergist and nutritionist will in this study use this assay for indication regarding what
227 foods to trial. If a food is falsely identified as safe by the assay but triggers a reaction, then these reactions
228 will be managed by the nutritionist and allergist as per current standard of care for failed trials.

229 Blood draw from infants and toddlers is a safe procedure with minimal risks. Trained and experienced
230 phlebotomists at UMHS perform blood draws on infants and toddlers routinely. The procedure may cause
231 anxiety for the infant/toddler. The test can result in a small bruise or mild soreness for the child at the site of
232 blood draw. The bruise can last for a few days.

233 A risk of breach of confidentiality always exists in all studies.

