234 **Describe alternate treatments and procedures**

235 The parent/child can proceed with introduction of new foods per guidance of the nutritionist. This is based
236 on historically better tolerated foods in the general FPIES population and may or may not apply to the
237 patient.

245 **2. Adequacy of protection against risks**

246 **A. Recruitment and Informed Consent**

249 Plan for recruitment

250 All FPIES patients will be recruited from the University of Michigan Allergy Clinics, and University of
251 Michigan Pediatric outpatient clinics. The patients will be identified by pre-screening of the UM FPIES
252 patient cohort. Pre-screening will be performed by members of the Division of Allergy and Immunology at
253 Michigan Medicine. Patients will not be contacted by the study team until pre-approval is obtained from the
254 primary allergist or pediatric clinician. Suitable FPIES patients who fulfill the inclusion and exclusion criteria
255 will be contacted by email and / or phone. An option to opt out will be provided. If patients are interested in
256 participating, a meeting with the study team will be scheduled at the UM allergy clinics. The patients will be
257 presented with the consent form by the study team member to consider consenting for the study and the
258 blood draw procedure. Patients will be told that their decision whether to participate in the study will not
259 affect their clinical care.

261 Describe the circumstances of consent

262 A study coordinator or clinical study team member familiar with the study protocol will obtain informed
263 consent for all participants. Consent/assent will be obtained prior to any study measures/questionnaires.
264 Each participant will receive a verbal and written explanation of the purposes, procedures, risks, and
265 potential benefits of the study in language appropriate for the individual.

266 **B. Protections Against Risk**

268 Planned procedures for protecting against risk

- 271 1. The risk of a false result will be managed by the allergist and nutritionist as per current standard of care in
272 managing reactions to failed trials.
- 274 2. The risk from blood draw is minimal and routinely performed by the phlebotomists at UMHS.
- 276 3. All data variables will be kept in a separate "Research Data" REDCap database. Subjects will be
277 identified only by subject number in this database.

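### Home food-trial results return to the study team only every 3 months while a new food can start every seven days, and no stated route takes a reaction to the research team or laboratory sooner

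*Combined protocol and SAP*

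**What the plan says.** All of this is in the combined protocol and SAP.

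- **Source of the calls.** Under Study Design, step 9, the investigator's research laboratory runs the assay. Under step 10 the result is "given to the clinical study team and child's clinician, who will contact parents by phone or email". Step 10b opens "After discussion within the clinical team (including clinical research team and child's" and goes on to include the child's own clinicians, so the instruction to parents is a joint one.
- **Pace.** Step 10b: called-safe foods enter "the diet, one at a time for seven days".
- **Return of results.** Step 10c: "Results of these trials will be recorded on Questionnaire Three and returned to the study" "team 3 month intervals". Step 12 uses the same interval: "Subjects will be followed at 3 month intervals with review of tolerated foods, number and types of" known triggers. The Study Grid also places Questionnaire 3 in the three-monthly column, for up to 36 months.
- **Risk.** Section I.1.C, Potential Risks: "The risk in this study arises due to incorrect predictions by the test".
- **Protection.** Section I.2.B: "The risk of a false result will be managed by the allergist and nutritionist as per current standard of care in" handling failed trials. Section I.1.C says the same, and adds that the allergist and nutritionist tell the family which foods to try.

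The documents describe no event-driven report of a reaction to the study team or laboratory, and no pooled review of called-safe foods that turn out to cause reactions.

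**The concern.** The plan names a wrong safe call as its main risk, but the only scheduled channel that would show such calls to the study team runs quarterly. Trials can run weekly. Standard-of-care management protects the child who reacts. It does not by itself correct an error in the assay or in a food preparation that also affects other children, because nobody is assigned to put reactions from different children together.

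A shared error is a possibility, not something the documents report. Specific aim 2 treats the reliability of standardized frozen foods against freshly prepared ones as an open question.

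The plan's reason for needing nothing further is also not consistent. Section I.4 argues that a wrong prediction cannot be riskier than random choice of foods. The passage on alternate procedures in section I.1.C says nutritionist guidance draws on foods that FPIES patients have historically tolerated better. Against that comparator a poor assay could do worse, and timely pooling is how the study would notice.

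The home-trial outcome also shows whether a called-safe food is truly safe, which is the binary outcome in the Statistical Design. The quality of this record therefore matters for the validation as well as for safety.

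**Working it through.** The plan gives no number of foods per reporting interval, so there is no figure of its own to reproduce.

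**Inputs from the documents:** seven days per food (step 10b); 3 months between returns (step 10c, step 12, Study Grid); more than 20 foods screened (Background); at least 2 known triggers per child (inclusion criteria).

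**Ceiling on trials per interval** = interval length / days per food.
- 90/7 = 12.9, which is 12 complete trials
- 91/7 = 13.0
- 92/7 = 13.1, which is 13 complete trials

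**Position of the wrong call.** If the first of 13 foods is the wrong one, up to 12 more can start before the scheduled return. If it is equally likely to be in any slot, the mean number still to come is (12 + 11 + … + 0)/13 = 78/13 = 6.

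**Gaps between foods (assumed).**
- 3 days: 91/(7 + 3) = 9.1 foods
- 7 days: 91/(7 + 7) = 6.5 foods

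**Length of the list (assumed).** The documents do not say how many foods are called safe. Take 20 foods screened, 2 to 6 of them triggers, 0 to 5 already known safe, and 50% to 100% of the rest called safe.
- Low end: (20 − 6 − 5) × 0.5 = 4.5 foods
- High end: (20 − 2 − 0) × 1.0 = 18 foods, limited to 13 by the calendar

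The count per interval therefore runs from about 4.5 to 13.

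**Chance that an interval contains at least one reaction.** The documents give no reaction rate for called-safe foods. With assumed rate r, independent foods and n trials completed without interruption, the chance is 1 − (1 − r)^n and the expected number is n × r.

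| r (assumed) | n = 13: expected | n = 13: at least one | n = 6: at least one |
|---|---|---|---|
| 10% | 1.3 | 75% | 47% |
| 20% | 2.6 | 95% | 74% |
| 30% | 3.9 | 99% | 88% |

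The n = 13 columns inherit the ceiling. Even at six foods per interval, a reaction between returns is far from rare at these rates.

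**Tracing a reaction through the text.** A reaction goes to the allergist and nutritionist (I.1.C, I.2.B). They and the child's clinician take part in instructing the family (step 10, step 10b, I.1.C). The next written step that brings the result to the study team is the quarterly form (step 10c) or the quarterly follow-up (step 12). No written step returns it to the laboratory before then.

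**The case against.** The strongest reply is that people close to the calls would already know. The child's clinician receives the assay result, sits in the group that decides the instruction, and belongs to the service that manages reactions. A reader might infer from step 10c that nobody involved in giving the calls learns of a wrong one for three months. The documents do not support that. What remains unwritten is the onward link to the research team as a whole and to the laboratory.

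Other readings also go too far:

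- **No clinician could see a pattern.** Recruitment is from one institution's allergy and pediatric clinics, with at most 20 children, and Study Design step 1 refers to a single clinic nutritionist. The same clinicians may see several participants. The gap is that no one is given the task of pooling.
- **Thirteen foods as the usual case.** This needs back-to-back trials, at least 13 called-safe foods and no pause after a reaction. Scaling it to the whole cohort would also need every child to be active in the same quarter, which the documents do not say.
- **Parents recalling three months at once.** Step 10c ties the interval to the return of the form. It does not say when entries are made, and the questionnaires are not in the file. Recall error is only a possibility.
- **A contradiction between the two intervals.** There is none. A weekly trial and a quarterly return can coexist; the issue is whether that return suits the stated risk.

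The consent pages are also absent from the file, so advice to parents about reporting reactions cannot be called missing. That does not remove the point, because step 10c itself sets the quarterly return.

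**Conclusion.** The concern holds in a limited form. Between scheduled returns, up to 13 seven-day trials per child can take place; under the assumptions above, about 4.5 to 13. During that time the documents specify no route or time limit for a reaction to reach the research team and the laboratory that generates the calls. An error common to several children could go unpooled for up to a quarter.

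The seven-day and 3-month intervals are in the text. The range of counts rests on assumed gaps and list lengths, and the reaction probabilities on assumed rates, independence and uninterrupted trials. The reporting gap depends on none of these assumptions. The sponsor should change it because the exposures occur at home in infants and young children, on the strength of a test that section I.1.C says is neither FDA-approved nor cleared. Nothing here shows that care of an individual reaction is inadequate.

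**What to change.** In step 10c, replace the 3-month return with one brief Questionnaire Three entry in the existing REDCap system at the end of each seven-day trial: date, food, tolerated or reacted. Have any suspected reaction notified promptly to the clinical study team and the laboratory, and state who sends the notice.

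Have the study team keep a running tally of reactions among called-safe foods, overall and by food, and look at it before each further child's list is released.

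Reconcile Study Design steps 10 and 12, the Study Grid, and sections I.1.C and I.2.B so that they describe the same reporting path.

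This changes data flow only. Any action on the tally and all care of individual reactions stay with the sponsor's clinicians; no hold threshold or clinical rule is proposed. If they do act on the tally, log the action and its date, because it can change which calls are tested in the validation.

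The cost is some protocol wording, a short form in a system already in use, and more frequent but shorter entries by parents.
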